On study tumor assessments	Tumor assessments that meet the following criteria: 1. No gap of ≥ 91 days between successive tumor assessments among those on or prior to the on study tumor assessment. (Note: a tumor assessment for which "Not Evaluated" is entered into the database does not qualify as a tumor assessment.) 2. No prior initiation of non-protocol anticancer therapy.
Overall response rate	The proportion of patients achieving a complete response or partial response to treatment.
Dose intensity	The total dose (in mg) a patient actually received divided by the total dose (in mg) the patient should have received had there been no missed doses, dosing delays or dosage reductions.
Intent-to-treat population	All patients randomized to receive study drug regardless of whether they actually received study drug and regardless of whether evidence is found indicating they failed to meet study inclusion/exclusion criteria or had other protocol violations.
Last contact date	The last contact date is the latest assessment/visit date recorded on any of the following case report forms: Discontinuation, Hematology, Chemistry, RECIST Overall Response Tumor Assessments, Survival Follow Up, Study Drug Infusion, Etoposide Infusion or Platinum Therapy Infusion.
Non-Protocol Anti-Cancer Therapy	Non-protocol anti-cancer therapies used by patients during their participation in this study, if any, will be identified by the sponsor after review of relevant data listings.
Per-protocol population	The subset of safety population who either (a) have at least one response evaluation on study, or (b) die prior to their first scheduled response evaluation.
Platinum Therapy / Platinum Choice	The physician's choice of platinum therapy (cisplatin or carboplatin) was used as a stratification variable by the dynamic randomization system. Discrepancies, if any, between the platinum therapy used to stratify a patient's treatment assignment and the platinum therapy actually administered during the study will be dealt with as follows. Platinum choice entered in the dynamic randomization system will be used in all efficacy analyses where platinum choice is included as a model

	effect. However, actual platinum received (as documented on earliest Platinum Therapy Infusion CRF [e.g., Cycle 1, Day 1]) will be used when calculating dosing compliance.

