3.1. Blinded Treatment Phase

Subjects who qualify for enrollment into the phase-2 portion of the study will be randomized in a 1:1 ratio to receive study treatment of EP with placebo or EP with tarextumab. The randomization will be balanced on the choice of platinum therapy (cisplatin versus carboplatin) and the prior use of whole brain radiation (WBR) or prophylactic cranial irradiation (PCI). Changing the choice of platinum therapy is not permitted once the subject is randomized. Treatment for each subject will begin on Cycle 1, Day 1 (the first dosing day). Etoposide 100 mg/m² will be given on Days 1, 2 and 3 and cisplatin 75 mg/m² or carboplatin to an AUC of 5 mg/mL/min will be given on Day 1 of every 21-day cycle for 6 cycles. Subjects may remain in the blinded treatment phase to continue one of the chemotherapy drugs if the other is held or discontinued prior to completing 6 cycles of EP and prior to disease progression. For subjects who have study drug held or discontinued for tolerability reasons, EP chemotherapy should continue to the completion of 6 cycles. Subjects may continue study drug if one or both of the chemotherapy drugs is held or discontinued prior to completing 6 cycles of EP and prior to disease progression.

After the completion of 6 cycles of EP, subjects who do not have disease progression and have not had WBR or PCI prior to study entry and are good candidates for PCI according to the

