According to the study design, administrations of randomized treatment (tarextumab or placebo only; without EP) may continue in 21-day cycles from the completion of 6 cycles of EP until the initiation of PCI. The following analysis of PFS will be conducted in order to determine if there is a treatment benefit when tarextumab is administered in combination with EP. Subjects who have not progressed will have their PFS censored 35 days (the scheduled time for 1 treatment cycle plus 7 days) following the last dose of Carboplatin/Cisplatin or EP. KM and Cox PH analyses will be the same as those described above.

The impact of the biomarkers Notch3, Hes1, Hey2, Hey1 and Hes6 on PFS will be evaluated with a Cox PH model with treatment, biomarker and treatment-by-biomarker interaction included in the model as independent variables. A separate Cox PH model will be used for each biomarker.

Sensitivity analyses for PFS include replicating the primary log-rank analysis using the PP population and unstratified log-rank tests using the ITT and PP populations.

The planned timing for the primary analysis of PFS is stated in section 5.5 above.

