8.3. Overall Response Rate

A patient's best overall response is defined as the best investigator-assessed RECIST response to treatment category recorded since the start of the treatment. The hierarchy of response ratings, best to worst, is CR, PR, SD, PD, followed by NE. The numbers and percentages of subjects achieving each of these response categories will be summarized within treatment group.

The ORR, defined as the proportion of patients achieving a CR or PR, and its 95% confidence interval will be computed within treatment group. The p-value for equality between treatment groups will be calculated for the two groups using a logistic regression model including treatment, platinum choice (cisplatin versus carboplatin) and prior treatment modality (WBRT or PCI) as categorical independent variables. Patients without any post-baseline tumor assessments will be classified among those never achieving a CR or PR.

The impact of the biomarkers Notch3, Hes1, Hey2, Hey1 and Hes6 on ORR will be evaluated with a logistic regression model with treatment, biomarker and treatment-by-biomarker interaction included in the model as independent variables. A separate logistic regression model will be used for each biomarker.

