8.6. Overall Survival

OS is defined as the number of days from randomization (Day 1) until death. The following rules will be used to define censored observations and censoring times for OS.

1. A patient for whom no death date is reported will have OS censored on the last contact date (defined on page 6). When evaluating the last contact date using the ‘Follow-Up After Discontinuation of Study Treatment’ CRF, both of the ‘date of survival assessment’ (if checked ‘alive’ for ‘subject status’) and the ‘last known survival date’ (if checked ‘alive or ‘lost to follow-up’ for ‘subject status’) will be considered.
2. Patients lacking data after randomization who do not die have their event time censored on the date of randomization with duration of 1 day.
3. All patients alive on the date of the 98th sequential patient death will have their OS censored on the day following the date on which the 98th patient died. All patient deaths will be counted towards the total of 98, independent of which treatment arm the deceased patients were randomized to.

The KM method will be used to estimate survival proportions over time. KM survival curves will be plotted and 95% confidence intervals for median OS will also be calculated for each treatment arm. The HR, its 95% confidence interval and the p-value for testing the statistical significance of the treatment effect will be generated using a Cox PH model with main effects for treatment, platinum choice (cisplatin versus carboplatin) and prior treatment modality (WBRT or PCI).

OS will also be analyzed separately for two subsets of ITT patients defined by platinum choice (cisplatin or carboplatin). In this case, the p-value for testing the statistical significance of the treatment effect will be generated using a Cox PH model with main effects for treatment and prior treatment modality only.

The impact of the biomarkers Notch3, Hes1, Hey2, Hey1 and Hes6 on OS will be evaluated with a Cox PH model with treatment, biomarker and treatment-by-biomarker interaction included in the model as independent variables. A separate Cox PH model will be used for each biomarker.

The planned timing for the primary analysis of OS is stated in section 5.5 above.

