It is noteworthy that high NOTCH3 is trending to be beneficial for patients with low N3RPI, whereas high NOTCH3 appears to be detrimental when N3RPI is high. This prompted the exploratory hypothesis that NOTCH 3 inhibition with tarextumab will improve PFS and OS in patients who have high N3RPI. In the case where N3RPI is high, tarextumab may be able to reduce the detrimental effects associated with high Notch 3 expression.

The following exploratory analyses will be carried out to test this hypothesis. The analysis population (ITT or per-protocol) will be divided into two N3RPI groups: High N3RPI and Low N3RPI (as defined above). Independent Cox PH models will be fit to data from each of the two groups. The models will include effects for treatment (tarextumab or placebo), NOTCH3 value, and the interaction between treatment and NOTCH3. The treatment HR and a 95% CI for the HR will be estimated at the quartiles of the NOTCH3 distribution. The same analysis will be carried out for “high” and “low” patient subgroups based on each of the biomarkers (Hes1, Hes6, Hey1 and Hey2).

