Note: Overall Survival = Date of Documentation of Death – Randomization Date + 1. Subjects who had not experienced death by their last contact date were censored at that time. Subjects lacking data after randomization who do not die have their event time censored on the date of randomization with duration of 1 day. For detailed event and censoring rules, refer to protocol section 13.5.4 and SAP section 8.6. C.I. = Confidence Interval. SE = Standard Error.

^[1] Sum of all individual follow-up times in days divided by 365.25.

^[2] Number of deaths / total follow-up time.

^[3] Hazard ratio, 95% C.I. and p-value from Cox proportional hazards model with main effects for treatment, platinum choice and prior treatment modality.

Programmer notes: (a) repeat this table using the per-protocol population

Table 14.2.1.3
Overall Survival for Subjects Receiving Cisplatin
ITT Population

	Placebo (N=xx)	Tarextumab (N=xx)
Platinum Choice ^[1]		
Cisplatin	xx (xx.x%)	xx (xx.x%)
Carboplatin	xx (xx.x%)	xx (xx.x%)
Total Follow-Up Time (person-years) ^[2]	xxx.x	xxx.x
Number of Subjects who Died	xx (xx.x%)	xx (xx.x%)
Number of Subjects who did not Die (Censored)	xx (xx.x%)	xx (xx.x%)
Hazard ^[3]	0.xx	0.xx
Kaplan-Meier Estimates: Quartiles [95% C.I.] (days)		
25 th Percentile	xxx [xxx,xxx]	xxx [xxx,xxx]
50 th Percentile	xxx [xxx,xxx]	xxx [xxx,xxx]
75 th Percentile	xxx [xxx,xxx]	xxx [xxx,xxx]
Kaplan-Meier Estimate (# at risk) [SE]		
180 Days	0.xx (xx) [x.xx]	0.xx (xx) [x.xx]
360 Days	0.xx (xx) [x.xx]	0.xx (xx) [x.xx]
40 Days	0.xx (xx) [x.xx]	0.xx (xx) [x.xx]
720 Days	0.xx (xx) [x.xx]	0.xx (xx) [x.xx]
Range (Subjects who Died) (days)	xxx, xxx	xxx, xxx
Range (All Subjects) (days)	xxx, xxx	xxx, xxx
Hazard Ratio [95% C.I.] ^[4]		x.xx [x.xx,x.xx]
P-value ^[4]		0.xxx

Note: Overall Survival = Date of Documentation of Death – Randomization Date + 1. Subjects who had not experienced death by their last contact date were censored at that time. Subjects lacking data after randomization who do not die have their event time censored on the date of randomization with duration of 1 day. For detailed event and censoring rules, refer to protocol section 13.5.4 and SAP section 8.6. C.I. = Confidence Interval. SE = Standard Error.

^[1]Analyses presented in this table include only subjects who received cisplatin. Percentages below the first set of rows are based on subjects who received cisplatin.

^[2] Sum of all individual follow-up times in days divided by 365.25.

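### Overall survival by platinum: section 8.6 defines the subsets by randomization stratum, but the ITT table shells define them by drug received

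*SAP*

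**What the plan says.** **Survival by platinum, SAP text.** Section 8.6 states: "OS will also be analyzed separately for two subsets of ITT patients defined by platinum choice (cisplatin or carboplatin"). The Definitions entry on platinum therapy identifies platinum choice as the physician's choice used to stratify randomization. For efficacy it sets this rule: "Platinum choice entered in the dynamic randomization system will be used in all efficacy analyses where platinum choice is included as a model" effect. The one use that entry gives for the platinum actually received is dosing compliance.

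**Survival by platinum, shells.** In Appendix B, Table 14.2.1.3 is headed as an ITT table and its first row is labelled as platinum choice. Its title, however, refers to subjects receiving cisplatin, and footnote [1] says "Analyses presented in this table include only subjects who received cisplatin". The percentages use that same denominator. Table 14.2.1.5 does the same for carboplatin, and the Appendix A titles repeat the received wording.

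**Biomarker models.** In section 8.1 the effect of each marker on PFS "will be evaluated with a Cox PH model with treatment, biomarker and treatment-by-biomarker interaction included in the model as independent variables". Section 8.6 has the same form for OS. Section 8.3 has the logistic version for response: "will be evaluated with a logistic regression model with treatment, biomarker and treatment-by-biomarker interaction". For the exploratory index and high/low marker groups, section 9 says: "The models will include effects for treatment (tarextumab or placebo), NOTCH3 value, and the interaction between treatment and NOTCH3". None of these contains platinum choice or prior cranial irradiation. The main PFS, OS, response, duration-of-response and tumour-length models contain both.

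**The concern.** Platinum choice is fixed before randomization, so tarextumab and placebo patients within one platinum stratum form a randomized comparison. Platinum received is known only afterwards. A table restricted on it is no longer an ITT analysis of the stratum, whatever its label says.

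Programmers build from shells. The reported result could therefore follow the received-drug rule while the study report cites section 8.6 for a different patient set. Section 6.1 defines ITT as all randomized patients whether or not they were dosed, so the shells also conflict with their own population label.

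The biomarker models raise a lesser question. They address a secondary objective in section 2.2 but drop the two stratification factors that the main models keep, and no reason is given.

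**Working it through.** **1. The two definitions side by side**

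| Item | Section 8.6 | Tables 14.2.1.3 and 14.2.1.5 |
|---|---|---|
| Population | ITT | ITT (header) |
| Subset variable | platinum choice | platinum received (title, footnote, denominator) |
| Randomized, no platinum given | in the table of the assigned stratum | in neither table |
| Drug differs from stratum | stays in the stratum | moves to the other table |

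The SAP foresees both ways in which the definitions diverge. Section 6 allows the data cut to be extended because some randomized patients may never start treatment. The Definitions section sets out how discrepancies between stratum and drug are handled, and section 7.1 plans a cross-table of the two (Table 14.1.1.2).

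**2. How many patients**

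No figure is stated, so this can only be bounded by inference.
- Patients behind the blinded model in section 9 (notes to Table 6): 89 + 56 = 145.
- Planned evaluable patients (section 3), meaning those given at least one dose of study drug: about 135.
- Excess: 145 − 135 = 10.

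If all of the excess were randomized and untreated, and so also received no platinum, about 10 patients would drop out of both tables. If the excess is simply over-enrolment of treated patients, the number is 0. Range: 0 to about 10, plus an unknown number of discrepant patients. Sections 3 and 3.1 do not permit a change of platinum after randomization, so that second number should be low.

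**3. Effect of adding the strata to the biomarker models**

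The SAP has no figure to reproduce here. The size was gauged by simulating 600 data sets per scenario. Assumptions: 89 patients allocated 1:1, true treatment HR 0.67 at the mean of a standard normal marker, interaction coefficient −0.3, platinum split 50/50, prior cranial irradiation in 20%, and the same HR for each stratification factor.

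| Assumed stratum HR | Median treatment HR, strata omitted | Strata included | Difference | Interaction coefficient, omitted / included |
|---|---|---|---|---|
| 1.0 | 0.665 | 0.663 | 0.002 | −0.316 / −0.335 |
| 1.5 | 0.672 | 0.642 | 0.030 | −0.293 / −0.307 |
| 2.0 | 0.691 | 0.665 | 0.026 | −0.291 / −0.328 |

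Omitting the strata pulls the treatment HR towards 1 by about 0.03 when they are prognostic. The interaction, which is the purpose of these models, changes little. These are orders of magnitude: the adjusted medians themselves range from 0.642 to 0.665 around a true 0.67.

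**4. Cost in parameters**

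Table 6 reports 58 events. Going from three to five parameters takes events per parameter from 58/3 = 19.3 to 58/5 = 11.6 in the whole marker set. In each half of a median split, assuming events divide evenly (58/2 = 29), it goes from 29/3 = 9.7 to 29/5 = 5.8. The final data will hold more events, and a single-marker model may keep more than 89 patients.

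**5. Background**

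The design figures are not in play. By the Schoenfeld formula at one-sided 0.15, 91 PFS events at HR 0.67 give power 0.809 (SAP 0.8090), and 98 deaths at HR 0.682 give 0.805 (SAP 0.8047).

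**The case against.** **On the survival tables.** The received wording may be a slip rather than a decision to analyse as treated. The body text is right, the shell row is labelled as platinum choice and the header is ITT. The exposure shell, Table 14.3.5.5, has a nearly identical footnote that may have been carried over. Switching is not permitted, few patients are likely to be affected, and blinding makes exclusion that differs by arm no obvious risk. All of this bears on size and intent. It does not remove the contradiction between section 8.6 and the shells.

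**On the biomarker models.** A reader might infer that the Definitions rule obliges every efficacy model to carry platinum choice. It does not. The sentence is limited to analyses in which platinum choice is already a model effect, so it allows for models without it. Text and shells agree on the biomarker models, so there is no contradiction.

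A reader might also infer that 39% of patients lack each marker (56/145 = 0.386). That fraction comes from one joint model of HES1, HES6 and NOTCH3; the planned models take one marker at a time, and Hey1 and Hey2 are not in Table 6. Nor does the marker subset lose the protection of randomization. The markers are baseline measures, so balance holds in expectation if missingness is unrelated to arm; only the tighter balance from dynamic allocation is lost. A 10-point imbalance in a factor with HR 1.5, both assumed, would shift the log HR by 0.10 × ln 1.5 = 0.04. The standard error is about 2/√58 = 0.26.

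**Conclusion.** The shells for Tables 14.2.1.3 and 14.2.1.5 contradict section 8.6 and their own ITT label, and should be corrected before programming. The effect is probably small: 0 to about 10 untreated patients, on the inference that the excess over planned dosed patients was never treated, plus an unstated number of discrepant patients.

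A reader might conclude more broadly that the plan disregards its randomization strata in efficacy analyses. The document does not support that. Section 8.6 uses the stratum correctly, and the primary PFS log-rank test is stratified on both factors.

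The missing strata in the single-biomarker models are an unexplained difference from the main models, not an error. Adding them is a cheap improvement with a mild expected effect. For the exploratory index and high/low models in section 9, sparse events per group are reason enough to leave them as they are.

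**What to change.** **Correction**
- Tables 14.2.1.3 and 14.2.1.5, with their Appendix A titles: reword title, footnote [1] and denominators so that the subset is all ITT patients whose platinum choice in the randomization system was cisplatin or carboplatin respectively.
- Tables 14.2.1.4 and 14.2.1.6: apply the same stratum definition within the per-protocol population. These cannot hold all ITT patients of a stratum.
- If a display by drug received is also wanted, make it a separate table labelled as such.

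The cost is shell and title wording. The stratum variable is already held for the main models.

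**Optional improvement**
- Add platinum choice and prior cranial irradiation to the single-biomarker PFS, response and OS models in sections 8.1, 8.3 and 8.6, and to the footnotes of Tables 14.2.1.7, 14.2.2.5 and 14.2.5.3; or state in a sentence why they are left out.
- Leave the section 9 models (Tables 14.2.1.9 and 14.2.2.7) unchanged.

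The cost is two covariates already in the database and two more parameters per model with limited events.

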8.2. Total Tumor Length

Total tumor length is the sum of the longest diameters (SLD) for the target lesions as defined by RECIST criteria. Standard summary statistics for a continuous variable (identified in section 5) will be computed for SLD at baseline and the Cycle-3, Day-1 (C3D1) and Cycle-5, Day-1 (C5D1) assessments. Summary statistics will also be presented for changes from baseline at the C3D1 and C5D1 tumor assessments. Ninety-five percent confidence intervals for the mean SLD at each time point will also be computed. Two analysis of covariance (ANCOVA) models for SLD will be used to test the hypothesis that there is no difference between treatment arms with regard to changes in tumor length from baseline at the C3D1 assessment.

- The difference between the follow-up and baseline SLD (e.g., $SLD_{C3D1} - SLD_{baseline}$) will be the dependent variable in the first ANCOVA model. Treatment, platinum choice (cisplatin versus carboplatin) and prior treatment modality (WBRT or PCI) will be categorical factors in the model, and $SLD_{baseline}$ will be included as a continuous covariate.
- The log of the ratio of follow-up to baseline SLD (e.g., $\log [SLD_{C3D1}/SLD_{baseline}]$) is the dependent variable in the ANCOVA model. Treatment, platinum choice and prior treatment modality will be categorical factors in the model, and $\log SLD_{baseline}$ will be included as a continuous covariate.

Missing values will not be imputed.

Separate but similar analyses will be performed for changes in tumor length from baseline at the C5D1 assessment.

A waterfall plot of best percent change in SLD across all tumor assessments relative to baseline will be presented.

Rates of change in SLD from baseline to C3D1, C5D1 and at progression will be evaluated.

The rate of change in SLD at CxD1 is defined as

$$100 \left(\frac{SLD_{CxD1} - SLD_{baseline}}{SLD_{baseline}} \right) / d_2$$

where d_2 is the number of days between the baseline assessment (Day 1) and the CxD1 assessment.

Rate of change in SLD at CxD1 will be missing for subjects who did not have a RECIST assessment corresponding to the CxD1 visit.

The rate of change in SLD from its on-study nadir to progression is defined as

$$100 \left(\frac{SLD_{progression} - SLD_{nadir}}{SLD_{nadir}} \right) / d_1$$

where d_1 is the number of days between the on-study SLD nadir and progression.

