Rate of change in SLD at progression will be missing for subjects who did not have a RECIST assessment of PD on study and for subjects whose on-study $SLD_{nadir} = 0$.

Comparisons of these rates of change between the two treatment arms will be made using an analysis of variance (ANOVA) model with treatment, platinum choice (cisplatin versus carboplatin) and prior treatment modality (WBRT or PCI) as categorical independent variables.

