Note: tumor length is calculated as the sum of the longest diameters (SLD) for the target lesions. SD = Standard Deviation; LS = Least Squares; SE = Standard Error; C.I. = Confidence Interval.

^[1] The difference between the follow-up and baseline SLD (e.g., $SLD_{C3D1} - SLD_{baseline}$) is the dependent variable in the ANCOVA model for change from baseline. Treatment, platinum choice (cisplatin versus carboplatin) and prior treatment modality (W/BRT or PCI) will be categorical factors in the model, and $SLD_{baseline}$ will be included as a continuous covariate.

^[2] The log of the ratio of follow-up to baseline SLD (e.g., $\log [SLD_{C3D1}/SLD_{baseline}]$) is the dependent variable in the ANCOVA model for percent change. Treatment, platinum choice and prior treatment modality will be categorical factors in the model, and $\log [SLD_{baseline}]$ will be included as a continuous covariate.

Programmer notes: (a) repeat this table using the per-protocol population

Table 14.2.4.3
Rate of Change in Total Tumor Length at Progression
ITT Population

	Placebo (N=xx)	Tarextumab (N=xx)
SLD at Nadir		
n	xx	xx
Mean (SD)	xx.x (xx.xx)	xx.x (xx.xx)
Median	xx	xx
25 th , 75 th Percentile	xx, xx	xx, xx
Min, Max	xx, xx	xx, xx
SLD at Progression		
n	xx	xx
Mean (SD)	xx.x (xx.xx)	xx.x (xx.xx)
Median	xx	xx
25 th , 75 th Percentile	xx, xx	xx, xx
Min, Max	xx, xx	xx, xx
Rate of SLD Change from Nadir to Progression (%/day) ^[1]		
N	xx	xx
Mean (SD)	xx.x (xx.xx)	xx.x (xx.xx)
Median	xx	xx
25 th , 75 th Percentile	xx, xx	xx, xx
Min, Max	xx, xx	xx, xx
P-value ^[2]		0.xxx

Note: SLD = Sum of Longest Diameters (i.e., total tumor length for target lesions as defined by RECIST criteria [version 1.1]).

^[1] Rate of Change in SLD at progression = 100 x (SLD at Progression – SLD at Nadir) / SLD at Nadir / (number of days between nadir and progression).

^[2] P-value for treatment effect from ANOVA model with treatment, platinum choice and prior treatment modality as categorical independent variables.

Programmer notes: (a) repeat this table using the per-protocol population

Table 14.2.4.5
Rate of Change from Total Tumor Length at Baseline
ITT Population

	Placebo (N=xx)	Tarextumab (N=xx)
SLD at Baseline		
n	xx	xx
Mean (SD)	xx.x (xx.xx)	xx.x (xx.xx)
Median	xx	xx
25 th , 75 th Percentile	xx, xx	xx, xx
Min, Max	xx, xx	xx, xx
SLD at Cycle 3, Day 1		
n	xx	xx
Mean (SD)	xx.x (xx.xx)	xx.x (xx.xx)
Median	xx	xx
25 th , 75 th Percentile	xx, xx	xx, xx
Min, Max	xx, xx	xx, xx

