Rate of SLD Change from Baseline to Cycle 3, Day 1 Assessment (%/day) ^[1]		
N	xx	xx
Mean (SD)	xx.x (xx.xx)	xx.x (xx.xx)
Median	xx	xx
25 th , 75 th Percentile	xx, xx	xx, xx
Min, Max	xx, xx	xx, xx
P-value ^[2]		0.xxx

Note: SLD = Sum of Longest Diameters (i.e., total tumor length for target lesions as defined by RECIST criteria [version 1.1]).

^[1] Rate of Change in SLD from baseline to CxD1 = 100 x (SLD at CxD1 – SLD at Baseline) / SLD at Baseline / (number of days between baseline and CxD1 assessment).

^[2] P-value for treatment effect from ANOVA model with treatment, platinum choice and prior treatment modality as categorical independent variables.

Programmer notes: (a) add rows for (i) SLD at Cycle 5, Day 1 and (ii) Rate of SLD Change from Baseline to Cycle 5, Day 1 Assessment; (b) repeat this table using the per-protocol population

Table 14.2.5.1
Best Overall Tumor Response Based on Investigator Assessment
ITT Population

	Placebo (N=xx)		Tarextumab (N=xx)	
	Response Rate	95% C.I. ^[2]	Response Rate	95% C.I. ^[2]
Best Overall Tumor Response ^[1]				
Complete Response (CR)	xx.x (xx.x%)	[xx.x, xx.x]	xx.x (xx.x%)	[xx.x, xx.x]
Partial Response (PR)	xx.x (xx.x%)	[xx.x, xx.x]	xx.x (xx.x%)	[xx.x, xx.x]
Stable Disease (SD)	xx.x (xx.x%)	[xx.x, xx.x]	xx.x (xx.x%)	[xx.x, xx.x]
Progressive Disease (PD)	xx.x (xx.x%)	[xx.x, xx.x]	xx.x (xx.x%)	[xx.x, xx.x]
Not Evaluable (NE)	xx.x (xx.x%)	[xx.x, xx.x]	xx.x (xx.x%)	[xx.x, xx.x]
No Post-Baseline Tumor Assessment Collected	xx.x (xx.x%)	[xx.x, xx.x]	xx.x (xx.x%)	[xx.x, xx.x]
Overall Response Rate (CR or PR)	xx.x (xx.x%)		xx.x (xx.x%)	[xx.x, xx.x]
Odds Ratio (Tarextumab/Placebo) ^[3]			x.xx	
P-value ^[3]			0.xxx	

^[1] Tumor response based on RECIST criteria (version 1.1).

^[2] Two-sided exact 95% C.I..

^[3] Odds ratio and p-value from logistic regression model including treatment, platinum choice and prior treatment modality as independent variables.

Programmer notes: (a) repeat this table using the per-protocol population

Table 14.2.5.3
Best Overall Tumor Response Based on Investigator Assessment – Impact of Biomarker Expression
ITT Population

Biomarker	Model Coefficients (SE) ^[1]		Odds Ratio [95% Confidence Interval] ^[1]			
	Treatment	Treatment x Biomarker Interaction	At 25 th Percentile	At 50 th Percentile	At 75 th Percentile	
Notch3	xx.x (xx.x)	xx.x (xx.x)	x.xx [x.xx,xx.xx]	x.xx [x.xx,xx.xx]	x.xx [x.xx,xx.xx]	
Hes1	xx.x (xx.x)	xx.x (xx.x)	x.xx [x.xx,xx.xx]	x.xx [x.xx,xx.xx]	x.xx [x.xx,xx.xx]	

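### The tests of the C3D1 and C5D1 rates of tumor-length change leave out baseline SLD, which the ANCOVAs of the same scans include: a small, free gain in precision is forgone on a supportive endpoint

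*SAP*

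**What the plan says.** Section 8.2 of the SAP defines the outcome and its time points: "Rates of change in SLD from baseline to C3D1, C5D1 and at progression will be evaluated". For the two scheduled visits the outcome is percent change per day. Table 14.2.4.5 footnote [1] gives "Rate of Change in SLD from baseline to CxD1 = 100 x (SLD at CxD1 – SLD at Baseline) / SLD at Baseline", and this is then divided by the number of days between the two assessments.

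On the test, section 8.2 states: "Comparisons of these rates of change between the two treatment arms will be made using an analysis of variance (ANOVA) model". The terms it lists are treatment, platinum choice and prior treatment modality, all categorical. Footnote [2] of Table 14.2.4.5 repeats them: "P-value for treatment effect from ANOVA model with treatment, platinum choice and prior treatment modality as categorical independent variables". The C5D1 rate is tested in the same shell, because the programmer note says to "add rows for (i) SLD at Cycle 5, Day 1 and (ii) Rate of SLD Change from Baseline to Cycle 5, Day 1 Assessment". The first block of that table summarizes "SLD at Baseline".

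Section 8.2 also plans two ANCOVAs of the C3D1 scans, with similar ones at C5D1. In the model for absolute change, baseline SLD "will be included as a continuous covariate". In the model for the log ratio of follow-up to baseline, log baseline SLD enters in the same way. Table 14.2.4.1 footnotes [1] and [2] confirm both, and footnote [2] makes the log-ratio model the source of the percent-change p-value.

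**The concern.** Baseline SLD is needed to compute the rate, so every patient in the analysis has it. The SAP adjusts for it elsewhere on the same scans and gives no reason for omitting it here.

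Dividing by baseline does not by itself remove dependence on baseline. Measurement error in the baseline scan enters the outcome, and initial tumor size may be related to relative shrinkage. The SAP's own log-ratio model shows the point: its outcome is also a ratio to baseline, and log baseline SLD is still a covariate.

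If the rate is correlated with baseline SLD, omitting it leaves avoidable residual variance. A chance difference in baseline SLD between the arms then passes into the rate comparison. Randomization (section 3.1) balances platinum choice and prior WBR or PCI, not tumor length.

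**Working it through.** **Inputs from the SAP.** Model terms: section 8.2 and the footnotes to Tables 14.2.4.1 and 14.2.4.5. Test level: two-sided 0.05, the default in section 5. Size: about 135 evaluable subjects (section 3), randomized 1:1 (section 3.1). The SAP gives no power, SD or baseline correlation for the rate, so there is no figure of its own to reproduce.

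**Assumed inputs.** Within-arm correlation r between rate and baseline SLD: |r| from 0 to 0.4. Patients with scans: 60 per arm, somewhat below half of 135.

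**Step 1: models side by side, same visits and scans**

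| Outcome | Baseline term |
|---|---|
| Absolute change (Table 14.2.4.1) | baseline SLD |
| Log ratio (Table 14.2.4.1) | log baseline SLD |
| Percent change per day (Table 14.2.4.5) | none |

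All three also contain treatment, platinum choice and prior treatment modality.

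**Step 2: precision.** Adding the covariate multiplies the residual variance by 1 − r². The equivalent gain in patients is 1/(1 − r²) − 1. The last column is the power the adjusted test would have where the ANOVA has 80%.

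| abs(r) | Variance removed | Equivalent extra patients | Power, from 80% |
|---|---|---|---|
| 0 | 0% | 0% | 80.0% |
| 0.1 | 1% | 1.0% | 80.4% |
| 0.2 | 4% | 4.2% | 81.6% |
| 0.3 | 9% | 9.9% | 83.6% |
| 0.4 | 16% | 19.0% | 86.4% |

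**Step 3: false-positive rate given an imbalance.** Let the arms differ by d = 0.3 SD in baseline SLD, with no treatment effect. Given the baselines, the ANOVA statistic has

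- mean r·d/√(2/n) = 0.3 × 0.3/√(2/60) = 0.09/0.1826 = 0.49
- variance 1 − r² = 0.91, so SD 0.954

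The upper tail is P(Z > (1.96 − 0.493)/0.954) = P(Z > 1.54) = 0.062. The lower tail is P(Z < −(1.96 + 0.493)/0.954) = P(Z < −2.57) = 0.005. The total is **6.7%**. The same formula gives 5.0% at r = 0, 5.2% at r = 0.1, 5.8% at r = 0.2 and 8.0% at r = 0.4.

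**Step 4: how often such an imbalance arises.** A difference of 0.3 SD is 0.3/0.1826 = 1.64 standard errors, and P(|Z| > 1.64) = 0.10.

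**Step 5: simulation check.** Trials of 120 patients were simulated under no treatment effect, with percent change per day as outcome, measurement error in both scans and 4,000 trials per setting. The stratification factors were left out of both models. Overall rejection was 4.5% to 5.0% for the ANOVA and 4.7% to 5.2% for the model with log baseline. Among trials with an imbalance above 0.3 SD, the ANOVA rejected in 8.4% at a correlation of −0.33 and 10.9% at −0.44, against 3.7% and 4.9% with adjustment. These conditional figures rest on roughly 10% of 4,000, or 400 trials each, so they are accurate only to a few percentage points. They also average over all imbalances above 0.3 SD and are not comparable with the 6.7% at exactly 0.3 SD. At a correlation near zero (−0.06), the two models had practically equal variance (ratio 1.004).

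**The case against.** The case for leaving the plan alone is substantial.

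- **Nothing is misstated.** Section 8.2 and the shell specify the same model, and an ANOVA on treatment and the randomization factors is a valid test in a randomized trial. This stands. A reader might infer inflated type I error or an internal contradiction; the documents support neither. Averaged over randomizations, the error rate is about 5%.
- **An adjusted analysis already exists.** The log-ratio ANCOVA covers both visits. Days to a scheduled scan should vary little, so the rate is close to rescaled percent change. This lowers the importance, but the rate comparison is a separate planned test with its own p-value, which Table 14.2.4.1 does not replace.
- **The gain rests on an assumption.** The outcome is already scaled by baseline, so r could be small, and at r = 0 nothing is gained. This stands, and the range above therefore starts at zero.
- **Disagreement between tables proves little.** A reader might attribute any difference between the rate and ANCOVA p-values to the missing covariate. The outcomes are on different scales (percent per day, log ratio, millimetres), so they could differ even with identical covariates.
- **No decision depends on it.** Rate of SLD change is in none of the objectives in section 2, and no power is claimed for it. This also stands.

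One numerical trap: treating the statistic in Step 3 as having unit variance gives P(|Z + 0.49| > 1.96) = 7.8%. That overstates the effect. Once baseline is held fixed its share of the variance is gone, and with unit conditional variance the overall variance would exceed 1, contradicting the validity of the test.

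**Conclusion.** The point holds as a minor improvement. The rate models at C3D1 and C5D1 omit a covariate that is already collected, complete in the analysed patients, and used by the SAP for the same scans even when the outcome is a ratio to baseline. The cost of the omission lies between nothing (r = 0) and precision equivalent to 19% more patients (|r| = 0.4), with weaker protection in the minority of trials where baseline tumor length happens to be unbalanced. These sizes depend on the assumed correlation and on 60 patients per arm; C5D1 will probably have fewer scans than C3D1. The primary and secondary conclusions are untouched.

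The point covers the C3D1 and C5D1 rates only. The nadir-to-progression rate in Table 14.2.4.3 carries the same footnote wording, but it is a different analysis with a different denominator, and nothing here bears on it.

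**What to change.** In section 8.2, split the sentence on comparing rates. For the C3D1 and C5D1 rates, specify an ANCOVA with treatment, platinum choice, prior treatment modality and log(SLD baseline) as a continuous covariate. Leave the model for the rate at progression as it is. Change footnote [2] of Table 14.2.4.5 to match, and add a row for the adjusted mean difference between arms beside its p-value.

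The log form follows the existing log-ratio model. The change costs one degree of freedom, a few words of text and one table row. It needs no new data and loses no patients, because the rate cannot be computed without baseline SLD. It should be made before database lock and unblinding, so that it counts among the analyses section 5 describes as defined in advance.
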